5.3.5.4 Abnormal Laboratory Values

Not every laboratory abnormality qualifies as an adverse event. A laboratory test result must be reported as an adverse event if it meets any of the following criteria:

- Is accompanied by clinical symptoms
- Results in a change in study treatment (e.g., dosage modification, treatment interruption, or treatment discontinuation)
- Results in a medical intervention (e.g., potassium supplementation for hypokalemia) or a change in concomitant therapy
- Is clinically significant in the investigator's judgment

It is the investigator's responsibility to review all laboratory findings. Medical and scientific judgment should be exercised in deciding whether an isolated laboratory abnormality should be classified as an adverse event.

If a clinically significant laboratory abnormality is a sign of a disease or syndrome (e.g., ALP and bilirubin $5 \times$ ULN associated with cholestasis), only the diagnosis (i.e., cholestasis) should be recorded on the Adverse Event eCRF.

If a clinically significant laboratory abnormality is not a sign of a disease or syndrome, the abnormality itself should be recorded on the Adverse Event eCRF, along with a descriptor indicating whether the test result is above or below the normal range (e.g., "elevated potassium," as opposed to "abnormal potassium"). If the laboratory abnormality can be characterized by a precise clinical term per standard definitions, the clinical term should be recorded as the adverse event. For example, an elevated serum potassium level of 7.0 mEq/L should be recorded as "hyperkalemia."

Observations of the same clinically significant laboratory abnormality from visit to visit should only be recorded once on the Adverse Event eCRF (see Section [5.3.5.3](#) for details on recording persistent adverse events).

5.3.5.5 Abnormal Vital Sign Values

Not every vital sign abnormality qualifies as an adverse event. A vital sign result must be reported as an adverse event if it meets any of the following criteria:

- Is accompanied by clinical symptoms
- Results in a change in study treatment (e.g., dosage modification, treatment interruption, or treatment discontinuation)
- Results in a medical intervention or a change in concomitant therapy
- Is clinically significant in the investigator's judgment

It is the investigator's responsibility to review all vital sign findings. Medical and scientific judgment should be exercised in deciding whether an isolated vital sign abnormality should be classified as an adverse event.

If a clinically significant vital sign abnormality is a sign of a disease or syndrome (e.g., high blood pressure), only the diagnosis (i.e., hypertension) should be recorded on the Adverse Event eCRF.

Observations of the same clinically significant vital sign abnormality from visit to visit should only be recorded once on the Adverse Event eCRF (see Section 5.3.5.3 for details on recording persistent adverse events).

5.3.5.6 Abnormal Liver Function Tests

The finding of an elevated ALT or AST ($>3 \times$ baseline value) in combination with either an elevated total bilirubin ($>2 \times$ ULN) or clinical jaundice in the absence of cholestasis or other causes of hyperbilirubinemia is considered to be an indicator of severe liver injury (as defined by Hy's Law). Therefore, investigators must report as an adverse event the occurrence of either of the following:

- Treatment-emergent ALT or AST $>3 \times$ baseline value in combination with total bilirubin $>2 \times$ ULN (of which $\geq 35\%$ is direct bilirubin)
- Treatment-emergent ALT or AST $>3 \times$ baseline value in combination with clinical jaundice

The most appropriate diagnosis or (if a diagnosis cannot be established) the abnormal laboratory values should be recorded on the Adverse Event eCRF (see Section 5.3.5.1) and reported to the Sponsor immediately (i.e., no more than 24 hours after learning of the event), either as a serious adverse event or an adverse event of special interest (see Section 5.4.2).

5.3.5.7 Deaths

All deaths that occur during the protocol-specified adverse event reporting period (see Section 5.3.1), regardless of relationship to study drug, must be recorded on the Adverse Event eCRF and immediately reported to the Sponsor (see Section 5.4.2). This includes death attributed to progression of CSU.

Death should be considered an outcome and not a distinct event. The event or condition that caused or contributed to the fatal outcome should be recorded as the single medical concept on the Adverse Event eCRF. Generally, only one such event should be reported. If the cause of death is unknown and cannot be ascertained at the time of reporting, "**unexplained death**" should be recorded on the Adverse Event eCRF. If the cause of death later becomes available (e.g., after autopsy), "unexplained death" should be replaced by the established cause of death. The term "**sudden death**" should not be used unless combined with the presumed cause of death (e.g., "sudden cardiac death").

If the death is attributed to angioedema or CSU, "angioedema" or "chronic spontaneous urticaria" should be recorded on the Adverse Event eCRF.

Deaths that occur after the adverse event reporting period should be reported as described in Section 5.6.

5.3.5.8 Preexisting Medical Conditions

A preexisting medical condition is one that is present at the screening (Day 1) visit for this study. Such conditions should be recorded on the General Medical History and Baseline Conditions eCRF.

A preexisting medical condition should be recorded as an adverse event only if the frequency, severity, or character of the condition worsens during the study. When recording such events on the Adverse Event eCRF, it is important to convey the concept that the preexisting condition has changed by including applicable descriptors (e.g., "more frequent headaches").

5.3.5.9 Lack of Efficacy or Worsening of Chronic Spontaneous Urticaria

Medical occurrences or symptoms of deterioration that are anticipated as part of CSU should be recorded as an adverse event if judged by the investigator to have unexpectedly worsened in severity or frequency or changed in nature at any time during the study. When recording an unanticipated worsening of CSU on the Adverse Event eCRF, it is important to convey the concept that the condition has changed by including applicable descriptors (e.g., "accelerated worsening of chronic spontaneous urticaria").

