5.2.1 Adverse Events

According to the ICH guideline for Good Clinical Practice, an adverse event is any untoward medical occurrence in a clinical investigation subject administered a pharmaceutical product, regardless of causal attribution. An adverse event can therefore be any of the following:

- Any unfavorable and unintended sign (including an abnormal laboratory finding), symptom, or disease temporally associated with the use of a medicinal product, whether or not considered related to the medicinal product
- Any new disease or exacerbation of an existing disease (a worsening in the character, frequency, or severity of a known condition) (see Sections [5.3.5.8](#) and [5.3.5.9](#) for more information)
- Recurrence of an intermittent medical condition (e.g., headache) not present at baseline

- Any deterioration in a laboratory value or other clinical test (e.g., ECG, X-ray) that is associated with symptoms or leads to a change in study treatment or concomitant treatment or discontinuation from study drug
- Adverse events that are related to a protocol-mandated intervention, including those that occur prior to assignment of study treatment (e.g., screening invasive procedures such as biopsies)

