5.3.5.10 Hospitalization or Prolonged Hospitalization

Any adverse event that results in hospitalization (i.e., inpatient admission to a hospital) or prolonged hospitalization should be documented and reported as a serious adverse event (per the definition of serious adverse event in Section 5.2.2), except as outlined below.

An event that leads to hospitalization under the following circumstances should not be reported as an adverse event or a serious adverse event:

- Hospitalization for respite care
- Hospitalization for a preexisting condition, provided that all of the following criteria are met:

The hospitalization was planned prior to the study or was scheduled during the study when elective surgery became necessary because of the expected normal progression of the disease

The patient has not experienced an adverse event

An event that leads to hospitalization under the following circumstances is not considered to be a serious adverse event, but should be reported as an adverse event instead:

- Hospitalization that was necessary because of patient requirement for outpatient care outside of normal outpatient clinic operating hours

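### Section 5.3.5.9 makes the reporting of serious CSU worsening, such as an unplanned admission for a flare or angioedema, depend on what the investigator expected

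*Combined protocol and SAP*

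**What the plan says.** Section 5.3.5.9 says that symptoms or deterioration of the kind foreseen in CSU "should be recorded as an adverse event if judged by the investigator to have unexpectedly worsened in severity or frequency"; a change in nature is a second trigger. Its next sentence, on how to word the entry, speaks only of the case "When recording an unanticipated worsening of CSU on the Adverse Event eCRF".

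Section 5.2.1 lists the things that an adverse event can be. One is "Any new disease or exacerbation of an existing disease (a worsening in the character, frequency, or severity of a known condition", and that bullet refers the reader on to 5.3.5.8 and 5.3.5.9. Section 5.3.5.8 says: "A preexisting medical condition should be recorded as an adverse event only if the frequency, severity, or character of the condition worsens during the study".

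Section 5.2.2 defines a serious adverse event as an adverse event that meets a listed criterion, inpatient hospitalization among them. Section 5.3.5.10 starts from the same place: "Any adverse event that results in hospitalization (i.e., inpatient admission to a hospital) or prolonged hospitalization should be documented" and reported as serious. It then exempts respite care, and admissions for a preexisting condition that were planned before the study or scheduled for elective surgery, provided the patient has had no adverse event.

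Section 5.3.5.7 requires every death in the reporting period to be recorded and reported, including deaths attributed to CSU. Section 5.3.5.11 says that safety analyses will not use patient-reported data and that sites need not review those data for adverse events.

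**The concern.** CSU is the one condition that every patient has, and it is the only one for which the protocol adds a test of expectedness. If that test decides whether a worsening is an adverse event at all, it also decides whether the seriousness criteria are ever applied. Two investigators with the same patient and the same admission could then report differently, each with support in the text.

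The incidence, nature, severity and timing of adverse events form the first endpoint under the primary safety objective (Section 2.1), and the study has no control arm against which uneven capture would show. Section 4.6.3 ties the sponsor's duty to stop the study to adverse event incidence and severity. Section 5.7 has the sponsor compare cumulative event frequency with the Investigator's Brochure. Both rely on consistent capture of serious events.

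**Working it through.** No arithmetic applies. The protocol gives no figure on this point, so the check sets the rules side by side.

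**1. Thresholds**

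| Section | What triggers an adverse event | Expectedness test |
|---|---|---|
| 5.2.1 | Exacerbation of an existing disease (*can* be an adverse event) | No |
| 5.3.5.8 | Worsening in frequency, severity or character (*only if*) | No |
| 5.3.5.9 | For CSU: unexpected worsening in severity or frequency, or a change in nature (*if*) | Yes |
| 5.3.5.7 | Death, including death from CSU or angioedema | No |

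For worsening in severity or frequency, the CSU rule is narrower than the two general ones.

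**2. Does the qualifier restrict?** If every worsening of CSU counted, the word *unexpectedly* would do no work. The following sentence gives recording guidance only for unanticipated worsening. The restrictive reading is the natural one, although the text does not say *only if*.

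**3. One case, two routes.** Take an unplanned admission for angioedema that the investigator considers typical of the patient's CSU.

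- *Through 5.3.5.9:* the worsening is not judged unexpected and its nature has not changed, so it need not be recorded. Sections 5.2.2 and 5.3.5.10 both start from an adverse event, so neither is reached. It adds 0 to the adverse event count and 0 to the SAE count.
- *Through 5.2.1, 5.3.5.8 and 5.3.5.10:* a known condition has worsened in severity and the patient was admitted. The admission was neither planned nor elective and was not respite care, so no exemption applies. It adds 1 to each count.

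**4. Does the exemption list settle it?** The exemption for preexisting conditions needs all its criteria to be met. An unplanned admission fails the first, so it is not exempt. But the rule from which it would be exempted covers only adverse events, and the second criterion asks whether an adverse event occurred, which returns the reader to 5.3.5.9. Section 5.3.5.10 implies that the admission is reportable; it does not say so.

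**5. Is there another route to capture?**

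- Diary item 6b (Appendix 2) lets a patient record a hospitalization for angioedema. The diary stops at Week 12 (Section 4.5.7.1), and 5.3.5.11 rules it out as a source of adverse events.
- The adverse events of special interest in 5.2.3 do not include worsening of CSU or angioedema.
- The UCT and PhyGA-LS (Appendices 3 and 4) rate control over 4 weeks and contain no item on admission.

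None of these replaces an SAE report.

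**The case against.** The strongest reply is that this is a general definition followed by a cross-referenced specific rule. Section 5.2.1 says what an adverse event *can* be and points to 5.3.5.9. Section 5.3.5.8 states a necessary condition, not a sufficient one. Section 5.3.5.9 says *if*, although the section just before it uses *only if*, and a change in nature is a second trigger. The narrow exemptions in 5.3.5.10 would have little purpose if unplanned admissions for a preexisting condition were already outside reporting. Judgment about non-fatal symptoms of the disease under study is also compatible with recording every death.

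Much of this stands. A reader might infer that the protocol makes such admissions neither adverse events nor SAEs by rule. No sentence says so, and the exemption list points the other way. A reader might also infer that 5.3.5.9 contradicts 5.2.1 and 5.3.5.8 outright; given *can*, *only if* and the cross-reference, it is a tension in wording.

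A further inference would be that rebound after stopping treatment goes unseen. The documents do not support that. Adverse events are collected until 4 weeks after the final dose (5.3.1). The UCT and PhyGA-LS, each with a 4-week look-back, are scheduled at the follow-up visit about 4 weeks after the last dose (Appendix 1). That investigators would call a relapse off drug expected is conjecture.

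The reply does not remove the ambiguity over serious events. It needs 5.3.5.10 to override a qualifier that 5.3.5.9 states expressly, and nothing in the text says that it does.

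**Conclusion.** The concern holds as an unresolved conflict between 5.3.5.9 and 5.3.5.10 over serious worsening of CSU. Section 5.3.5.9 sets a narrower, judgment-based threshold for the study disease, and the SAE rules are conditional on passing it. Whether an unplanned admission for an anticipated flare or angioedema enters the adverse event and SAE counts therefore depends on the investigator's expectation.

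The conclusion assumes that at least some investigators will take *unexpectedly* as a restriction, which is its natural meaning. The size cannot be given: the documents state no rate of admission for flares or angioedema and no rate at which investigators would judge them anticipated. Any count or percentage would be invented. Each affected admission is counted once or not at all. The point merits a change because it bears on serious events under the primary safety objective and is easy to settle before data accrue.

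**What to change.** Reconcile 5.3.5.9 with 5.2.1, 5.2.2 and 5.3.5.10 by adding one sentence to 5.3.5.9:

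> Worsening of CSU or angioedema that meets a seriousness criterion in Section 5.2.2 is recorded as an adverse event and reported as an SAE whether or not it was expected.

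This brings non-fatal serious outcomes into line with the existing treatment of deaths in 5.3.5.7. It leaves investigator judgment in place for non-serious fluctuation of the disease, so ordinary CSU symptoms do not flood the safety tables. It changes no treatment, visit or assessment. The cost is a one-sentence amendment and a few more SAE reports with their eCRF entries.

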5.3.5.10 Hospitalization or Prolonged Hospitalization

Any adverse event that results in hospitalization (i.e., inpatient admission to a hospital) or prolonged hospitalization should be documented and reported as a serious adverse event (per the definition of serious adverse event in Section 5.2.2), except as outlined below.

An event that leads to hospitalization under the following circumstances should not be reported as an adverse event or a serious adverse event:

- Hospitalization for respite care
- Hospitalization for a preexisting condition, provided that all of the following criteria are met:

The hospitalization was planned prior to the study or was scheduled during the study when elective surgery became necessary because of the expected normal progression of the disease

The patient has not experienced an adverse event

An event that leads to hospitalization under the following circumstances is not considered to be a serious adverse event, but should be reported as an adverse event instead:

- Hospitalization that was necessary because of patient requirement for outpatient care outside of normal outpatient clinic operating hours

5.3.5.11 Patient-Reported Outcome Data

Adverse event reports will not be derived from PRO data by the Sponsor, and safety analyses will not be performed using PRO data. Sites are not expected to review the PRO data for adverse events.

5.4 IMMEDIATE REPORTING REQUIREMENTS FROM INVESTIGATOR TO SPONSOR

Certain events require immediate reporting to allow the Sponsor to take appropriate measures to address potential new risks in a clinical trial. The investigator must report such events to the Sponsor immediately; under no circumstances should reporting take place more than 24 hours after the investigator learns of the event. The following is a list of events that the investigator must report to the Sponsor within 24 hours after learning of the event, regardless of relationship to study drug:

- Serious adverse events (defined in Section 5.2.2; see Section 5.4.2 for details on reporting requirements)
- Adverse events of special interest (defined in Section 5.2.3; see Section 5.4.2 for details on reporting requirements)
- Pregnancies (see Section 5.4.3 for details on reporting requirements)
- Overdoses, medication errors, drug abuse, or drug misuse (see Section 5.4.4 for details on reporting requirements)

The investigator must report new significant follow-up information for these events to the Sponsor immediately (i.e., no more than 24 hours after becoming aware of the information). New significant information includes the following:

- New signs or symptoms or a change in the diagnosis
- Significant new diagnostic test results
- Change in causality based on new information
- Change in the event's outcome, including recovery
- Additional narrative information on the clinical course of the event

Investigators must also comply with local requirements for reporting serious adverse events to the local health authority and Institutional Review Board or Ethics Committee (IRB/EC).

5.4.2 Reporting Requirements for Serious Adverse Events and Adverse Events of Special Interest

5.4.2.1 Events That Occur prior to Study Drug Initiation

After informed consent has been obtained but prior to initiation of study drug, only serious adverse events caused by a protocol-mandated intervention should be reported. The paper Clinical Trial Serious Adverse Event/Adverse Event of Special Interest Reporting Form provided to investigators should be completed and submitted to the Sponsor or its designee immediately (i.e., no more than 24 hours after learning of the event), either by faxing or by scanning and emailing the form using the fax number or email address provided to investigators.

5.4.2.2 Events That Occur after Study Drug Initiation

After initiation of study drug, serious adverse events and adverse events of special interest will be reported until 4 weeks after the final dose of study drug. Investigators should record all case details that can be gathered immediately (i.e., within 24 hours after learning of the event) on the Adverse Event eCRF and submit the report via the electronic data capture (EDC) system. A report will be generated and sent to Safety Risk Management by the EDC system.

In the event that the EDC system is unavailable, the paper Clinical Trial Serious Adverse Event/Adverse Event of Special Interest Reporting Form provided to investigators should be completed and submitted to the Sponsor or its designee immediately (i.e., no more than 24 hours after learning of the event), either by faxing or by scanning and emailing

the form using the fax number or email address provided to investigators. Once the EDC system is available, all information will need to be entered and submitted via the EDC system.

Instructions for reporting serious adverse events that occur >4 weeks after the final dose of study treatment are provided in Section 5.6.

5.4.3 Reporting Requirements for Pregnancies

5.4.3.1 Pregnancies in Female Patients

Female patients of childbearing potential will be instructed to immediately inform the investigator if they become pregnant during the study or within 4 weeks after the final dose of study drug. A paper Clinical Trial Pregnancy Reporting Form should be completed and submitted to the Sponsor or its designee immediately (i.e., no more than 24 hours after learning of the pregnancy), either by faxing or by scanning and emailing the form using the fax number or email address provided to investigators. Pregnancy should not be recorded on the Adverse Event eCRF. The investigator should discontinue study drug and counsel the patient, discussing the risks of the pregnancy and the possible effects on the fetus. Monitoring of the patient should continue until conclusion of the pregnancy. Any serious adverse events associated with the pregnancy (e.g., an event in the fetus, an event in the mother during or after the pregnancy, or a congenital anomaly/birth defect in the child) should be reported on the Adverse Event eCRF. In addition, the investigator will submit a Clinical Trial Pregnancy Reporting Form when updated information on the course and outcome of the pregnancy becomes available.

5.4.3.2 Pregnancies in Female Partners of Male Patients

Male patients will be instructed through the Informed Consent Form to immediately inform the investigator if their partner becomes pregnant during the study or within 4 weeks after the final dose of study drug. A paper Clinical Trial Pregnancy Reporting Form should be completed and submitted to the Sponsor or its designee immediately (i.e., no more than 24 hours after learning of the pregnancy), either by faxing or by scanning and emailing the form using the fax number or email address provided to investigators. Attempts should be made to collect and report details of the course and outcome of any pregnancy in the partner of a male patient exposed to study drug. When permitted by the site, the pregnant partner would need to sign an Authorization for Use and Disclosure of Pregnancy Health Information to allow for follow-up on her pregnancy. If the authorization has been signed, the investigator should submit a Clinical Trial Pregnancy Reporting Form when updated information on the course and outcome of the pregnancy becomes available. An investigator who is contacted by the male patient or his pregnant partner may provide information on the risks of the pregnancy and the possible effects on the fetus, to support an informed decision in cooperation with the treating physician and/or obstetrician.

